### Statistical Analyses

Treatment effects will be analyzed using ANCOVA and mixed regression models that may be flexibly adjusted according to the dependency structure in the repeated data.

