## Teaching Recovery Techniques: An Effective Short-term Intervention

Teaching Recovery Techniques (TRT) is a manualized, short term, group based intervention, which specifically focuses on children's symptoms of PTSD. TRT was developed by experts of the Children and War Foundation (C&W; [www.childrenandwar.org](http://www.childrenandwar.org)) to heal children's mental reactions to war and disaster-related trauma [29]. The aim of the intervention is to teach children self- help methods, by increasing perceptions of control and self-efficacy in relation to trauma symptoms, based on recommended and evidence based CBT- methods for trauma relief. The five sessions help students to understand the causes of trauma and recognize signs and symptoms. Adolescents are taught a range of coping skills to stop flashbacks and other intrusive images, sounds, or smells. Student hyperarousal is addressed through stabilization and relaxation techniques, and phobic avoidance behavior is gradually desensitized through use of relaxation with anxiety and anger hierarchies.

The program is delivered to groups of 5 - 15 adolescents by local group-leaders in pairs that are trained by representatives from C&W.

TRT has proven to be effective in reducing trauma-related mental health symptoms in contexts of war and disaster when delivered by non-clinicians and "lay" people [30-35]. However, TRT has rarely been implemented with UMA or URM in post-war contexts, who have a longer time span since the traumatic exposure than children in contexts of war, and who are experiencing additional psychosocial challenges. A small study conducted in the

U.K., showed more beneficial mental health effects among refugees than asylum-seekers, and the authors speculated if experiences of post-migration stressors might have reduced the effectiveness in the latter group [36]. A small pilot study in Sweden yielded positive effects of TRT among 48 UMA and URM.

In spite of the focus of TRT to increase coping and self-efficacy, none of the above mentioned studies included any measures of QoL-related constructs. To enhance our knowledge of the effectiveness of TRT in post-war contexts, we expand on the designs of the referred studies by 1) including a wait-list control group; 2) examining longer term effects; 3) including QoL-related outcomes (subjective wellbeing and self-efficacy) in addition to symptoms of PTSD, and 4) taking the psychosocial context into consideration.

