### Sample

The study involves about 170 UMA and URM  $> 8$  years.

Recruitment involved inviting reception centers and municipalities from all over Norway to participate as a first step. The children in the centers and municipalities that accepted to participate who spoke Pashto, Dari, Arabic, Somali or Tigrinya, were then invited to

participate (see information below).

A total of 18 TRT-groups have been conducted during the project period. To avoid cross-contamination [37] of the intervention, the children were allocated to Intervention or Control groups on an institutional level. We endorsed half of the participating reception centers and resettlement municipalities to Intervention Groups, and the other half to wait-list Control Groups. We did this based on practical considerations related to the data collection, such as time frames of the commission, geographical location of the targeted centers and municipalities, and availability of bilingual research assistants. The Intervention Groups started the TRT soon after the information meeting, and the Control Groups started when they had completed the five weekly sessions and the W2 data collection.

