### **Overview of the recruitment process**

Invitation to participate in the study was sent to reception centers and resettlement municipalities, and health nurses of the local primary health care, based on contact information from the three commissioning directorates. Centers / municipalities that agreed to participate assigned a contact person that assisted the research team in the information and recruitment stages of the project. They typically approached the largest language groups in their respective institutions. The research team sent out brief, written information and sound tracks about the project in the respective languages to the children, with an invitation to attend an information meeting. We also invited their legal guardians (representatives), and the TRT-group leaders to the information meeting, where we presented the intervention and the project, with the support of bilingual research assistants in the role as translators.

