### **Procedures**

Treatment response was registered by self-report questionnaires administered before upstart of TRT (W1), two weeks after the completion of TRT (W2) and two months after completion of TRT (W3). The questionnaires were translated to the participants' respective languages by standardized back-translation procedures. The children filled in the questionnaires in a group setting. The trained bilingual research assistants read the questions to the children, and assisted them with language issues.

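### Arms were set by institution and TRT was given in groups, but no institution or group term is specified; without one, the standard error is too small wherever children in an institution stay correlated in the fitted contrast

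*Combined protocol and SAP*

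**What the plan says.** On allocation, the Sample section states that "the children were allocated to Intervention or Control groups on an institutional level", with half of the participating institutions going to each arm. On how institutions were assigned it says: "We did this based on practical considerations related to the data collection".

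On delivery, the section introducing Teaching Recovery Techniques says: "The program is delivered to groups of 5 - 15 adolescents by local group-leaders in pairs". The Sample section adds: "A total of 18 TRT-groups have been conducted during the project period". That total appears to cover both arms, because wait-listed children received TRT later: "the Control Groups started when they had completed the five weekly sessions and the W2 data collection".

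On analysis, the Statistical Analyses section is one sentence, naming "ANCOVA and mixed regression models that may be flexibly adjusted according to the dependency structure in the repeated data". The Power section mentions linear mixed models and structural equation modelling, but gives no ICC, design effect or cluster term. Ethical Aspects refers to a larger approved study whose protocol is not among the documents.

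**The concern.** Arm is constant within institution, so differences between institutions add directly to the error of the arm comparison. The only dependency that the plan names is between waves in the same child. Modelling that does not make children in one institution independent of each other.

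The documents give reasons to expect correlation within institutions. In both arms there is the shared setting and often a shared language (of the contact persons: "They typically approached the largest language groups in their respective institutions"). There is also shared data collection ("The children filled in the questionnaires in a group setting", with assistants reading the items aloud). In the intervention arm at W2 there is, in addition, the shared TRT group and leader pair.

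At stake is the primary hypothesis, TRT against wait-list. If the correlation is positive and ignored, the confidence interval is too narrow and a true null is rejected too often.

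**Working it through.** **The plan's own figure.** The Power section gives n=150, d=0.40, alpha 0.05 and power 0.80. With independent children and no baseline adjustment, d·√(n/4) = 0.40·√37.5 = 2.449. Power is then Φ(2.449 − 1.960) = 0.688 two-sided, or Φ(2.449 − 1.645) = 0.789 one-sided. With ANCOVA and an assumed W1–W2 correlation of 0.5, 0.40/√(0.75·4/150) = 2.828 and two-sided power is Φ(2.828 − 1.960) = 0.807. The stated figure can therefore be reached, but each route treats children as independent.

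**Inputs for the clustering check.** About 170 children and 18 TRT groups come from the Sample section. The number of institutions is not given, so 12, 18 and 24 are assumed. The ICC is not given, so 0.01, 0.05 and 0.10 are assumed. W2 is used because it is the wave with an untreated comparison; Aims names no primary time point.

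**ANCOVA without a cluster term.** Here the ICC is that of W2 given W1. With m = 170/k children per cluster, DE = 1 + (m − 1)·ICC, and the actual two-sided error is 2·[1 − Φ(1.96/√DE)].

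| Clusters k | m | DE at ICC 0.01 / 0.05 / 0.10 | Actual error at nominal 5% |
|---|---|---|---|
| 24 | 7.08 | 1.061 / 1.304 / 1.608 | 5.7% / 8.6% / 12.2% |
| 18 | 9.44 | 1.084 / 1.422 / 1.844 | 6.0% / 10.0% / 14.9% |
| 12 | 14.17 | 1.132 / 1.658 / 2.317 | 6.5% / 12.8% / 19.8% |

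Simulation of ANCOVA with 18 clusters of unequal size (5 to 15) gave 6.0%, 10.9% and 16.4%. If only the intervention arm were clustered (18 equal clusters), the average DE is (1 + DE)/2 = 1.042, 1.211 and 1.422, and the error is 5.5%, 7.5% and 10.0%. That is a best case, since two of the sources above act in both arms.

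**Mixed model of W1 and W2 with a child intercept only.** Write the institution part of a score as a constant effect u plus a wave-specific effect v. The W1-to-W2 change removes u and keeps v. ANCOVA subtracts only b times W1, so (1 − b)·u remains. With total variance 1, b = 0.5 and u taking 5% of the variance, ANCOVA keeps 0.25·0.05/0.75 = 0.017 as its ICC, while the change contrast keeps 0.

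Simulation with 18 clusters of 9 children shows the difference:

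| Institution variance | ANCOVA, no cluster term | Change contrast (child-intercept model) |
|---|---|---|
| none | 4.9% | 5.0% |
| constant 5% | 6.4% | 4.9% |
| constant 10% | 8.4% | 5.4% |
| constant 20% | 11.2% | 5.0% |
| constant 5% + by-wave 2.5% | 10.7% | 10.0% |
| constant 5% + by-wave 5% | 14.4% | 14.8% |

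The last two change-contrast rows agree with the formula. The ICC of the change is 0.025/(0.025 + 0.475) = 0.05 and 0.05/(0.05 + 0.45) = 0.10. DE is then 1 + 8·0.05 = 1.4 and 1 + 8·0.10 = 1.8, and the error is about 9.8% and 14.4%.

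**Do the remedies hold?** A t test on baseline-adjusted institution means with k − 2 df ran at 4.9% to 5.8% in every configuration simulated. A REML random intercept for institution with k − 2 df never exceeded 5% (2.4% to 4.9%) and was conservative at small ICC.

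**The case against.** The strongest reply has four parts.

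- **A mixed model can carry an institution term.** True: the wording does not exclude one. But nothing commits to it, ANCOVA as named has none, and data collection is already complete, so the choice would be made with the data in hand.
- **The error does not arise under every model.** This stands. A reader might infer that any positive institution ICC invalidates whichever analysis is run. The documents do not support that: the plan names two methods, and in a child-intercept model of W1 and W2 a stable institution effect cancels. Shared language may be largely of that kind. A shared TRT group and leader pair need not be, because it acts between W1 and W2 in one arm only.
- **The size is unknown.** This also stands. The documents give no ICC, no number of institutions and no mapping of the 18 groups to institutions, and at ICC 0.01 the excess is about one percentage point. The 6% to 20% range should not be read as this trial's false-positive rate. It further assumes institution effects that are exchangeable between arms, whereas institutions were assigned on practical grounds.
- **The parent protocol may cover it.** Possibly. It is not supplied, and Statistical Analyses does not refer to it, so the accurate statement is that the supplied text specifies no such term.

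**Conclusion.** The point holds in conditional form, and should be fixed before the primary analysis. Run without a term for institution or TRT group, the planned comparison understates its standard error whenever children in one institution remain positively correlated in the fitted contrast. For ANCOVA any positive correlation in W2 given W1 suffices; for the child-intercept mixed model, institution-by-wave variance is needed.

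The error rates tabulated for 12, 18 and 24 clusters apply to ANCOVA only, and rest on the assumed ICCs and cluster numbers, equal cluster sizes and exchangeable institution effects. The gap in the plan does not depend on those assumptions; its size does.

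A reader might also infer that a cluster term would make the comparison sound. It would not: correct standard errors are necessary, but do not remove bias from the way institutions were assigned.

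**What to change.** In Statistical Analyses, state that the arm comparison will account for institution, with small-sample inference based on the actual number of institutions. Two workable forms are:

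- W2 on arm and W1, with a random intercept for institution and between-institution degrees of freedom;
- a t test on baseline-adjusted institution means.

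If waves are modelled jointly, include institution-by-wave variation, since a constant institution intercept does not protect the change contrast. Do not rest the primary conclusion on ANCOVA that ignores clusters. Report the number of institutions per arm and the ICC.

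**Cost.** This is a wording change, plus an institution identifier for each child; the documents do not say whether one is recorded. Intervals widen. Using the plan's n=150 and d=0.40, with an assumed W1–W2 correlation of 0.5 and 18 institutions (16 df, noncentral t), power is about 0.73, 0.62 and 0.52 at ICC 0.01, 0.05 and 0.10, against 0.81 under independence. With 170 children the figures are 0.78, 0.66 and 0.55 against 0.85. They move with the correlation: at n=150, a value of 0.3 gives 0.64, 0.54 and 0.45, and 0.6 gives 0.79, 0.69 and 0.59. They assume equal clusters and an exact-size test, so the conservative random-intercept form may have somewhat less power. The loss reflects allocation by institution, not the change of wording.

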## Relevance and Utility

Developing evidence based interventions to promote the mental health of asylum-seeking and refugee children is highly relevant to major mental health policies and practices. According to an analysis of the health services' psychosocial follow-up of asylum-seekers, [11], only 18% of the specialist mental health services report to have special competence with refugees. Moreover, a high proportion of the municipalities' primary health care experience challenges in collaborating with the specialist services, related to lacking capacity and competence, declined referrals, or that the refugee group is not prioritized (Rambøll, 2016). Evidence based, low threshold selective interventions that can be implemented outside Child and Adolescent Mental Health services, are therefore highly needed. Implementing low-threshold interventions is in line with the Government's strategy to improve the mental health of children and adolescents, which specifically mentions unaccompanied asylum-seeking and refugee minors [13] [12]. The Governments states that low-threshold interventions should be implemented early to avoid the development of serious mental disorders. Offering TRT to asylum-seeking children and young refugees in the early stages of the resettlement process (p. 48), is in accordance with these claims. Immigrant health and evaluation of mental health

promoting interventions that may contribute to better health services for refugees and other traumatized children and youth are important targets in the NIPH strategy [43].

## User Groups

At the upstart of the evaluation study, we established a user group of 3 unaccompanied minor asylum-seekers that we have met with 3 times, with one last meeting scheduled in May 2018. In the first meeting we informed about the project and discussed the role of the user group. We also discussed the stressors that asylum-seeking minors experience during their stay in reception centers. Based on this, we developed a checklist of asylum-stressors that we presented to the user group to get their feedback in the second meeting. They also gave input and advice to the content and structure of information we were to use in recruiting of asylum-seeking and refugee participants to the project. In the third meeting we discussed what traumatic events that are relevant and typical to unaccompanied minors, as a basis for the development of a revised checklist of traumatic experiences. The plan for the upcoming final meeting, is to get the users' perspectives on what they consider important topics for future grant proposals.

For the purpose of the proposed PhD study, we will establish a new user group, comprising 3 – 4 unaccompanied minors that has received residence in Norway. We will meet once or twice annually to discuss study questions and interpret the results of the analyses.

## Progress Plan

Project period: 20.06.2017- 31.12.2021

2017 – 2018 activities: Recruitment, intervention, data collection. Completed

2019 – 2021 activities: establish and meet with user group. PhD courses. Analyze data and write 5 articles

## Implementation of Research Findings

The main target groups for popular scientific dissemination of results are policy-makers and immigrant-refugee non-governmental organizations, asylum-seeking or refugee children and youth. The NIPH Department of Communication will be involved in planning strategies for communication with these groups through our traditional channels. We will collaborate with the C&W in producing popular scientific reports and fact sheets that can be easily available on various websites. Moreover, we will collaborate with the directorates that commissioned the evaluation study in organizing conferences and seminars to communicate research findings both to the local agents in charge of the care and support of refugee and asylum-seeking minors, and to local primary mental health care service providers.

## Ethical Aspects

The proposed PhD study is part of a more comprehensive study to implement and evaluate TRT that has been approved by REK (2016/355). The study protocol that was approved addressed main issues related to doing research in vulnerable asylum-seeking and refugee child populations.

## Collaboration with the Council of Mental Health (CMH)

The proposed study is well within the Strategic Plans of the CMH, what regards the focus on promoting the mental health of children and youth, information about refugee population's mental health, and the focus on low threshold intervention. Project coordinator [name], CMH, has provided us with valuable input regarding important issues to include in the proposal. She has read a draft of and given feedback to the study protocol. We have discussed a potential collaboration in relation to the progress of the study, the dissemination of important research findings should the study be granted, and how the specific competence of the study team can be made available to the CMH if needed.

